10.2.3.2 Patients' Evaluability for Response

All patients who have completed at least one evaluable cycle or who have received two uncompleted cycles followed by at least one response assessment not less than eight weeks (\pm one week) after treatment onset, will be considered evaluable for response. In addition, any eligible patients who receive at least one treatment cycle or have received two uncompleted cycles and experience disease progression or die due to progressive disease prior to response evaluation will be considered evaluable for response and will be categorized as an "early progression".

Patients withdrawn due to drug-related toxicity without any tumor assessments after the start of study treatment will be considered as "treatment failures".

Patients withdrawn due to significant clinical deterioration of unknown reason, hypersensitivity reactions, or refusal to continue on study for any reason or unrelated AEs without any disease assessments after the start of study treatment will be considered not evaluable for efficacy and their response will be categorized as "non evaluable".

Binomial estimates with exact 95% CIs will be calculated for the analysis of response rate. Randomized patients not evaluable for response will be excluded from the denominator exclusively for the futility analysis but will be included in all final efficacy analyses.

10.2.3.3 Final PFS Analysis and Interim OS analysis

The final PFS analysis will be performed when at least 210 progression or death events are observed.

The PFS assessed by the Independent Review Committee (IRC) will be used for the primary analysis, while the Investigator assessment will be used for the secondary analysis of PFS.

The unstratified log rank test will be used to compare the PFS of Arm A and Arm B.

Secondary time-to-event endpoints (DR, OS) will be analyzed according to the Kaplan-Meier method and compared between treatment groups using the log-rank test. A stratified log-rank test for the main endpoint (PFS) will be performed as supportive analysis. Both the IRC and Investigator's assessments will be used.

Counts and percentages, with their corresponding exact 95% confidence intervals, will be calculated for the RR (IMWG criteria and, separately, minor response). The Fisher's exact test will be used to compare the response rates of the Arm A and B.

10.2.3.4 Evaluation of Overall Survival

Although the study is powered for the evaluation of the main endpoint, PFS, two analyses of OS will be performed to ascertain if a trend in OS is observed in favor of the experimental arm. An interim analysis of OS will be performed concomitantly with the final PFS analysis (see Section 10.2.3.3). A final analysis of OS will be performed when 80% of death events (approximately 200 death events) have occurred or 24 months after the inclusion of the last patient, whichever occurs first. At the interim OS analyses, the significance level determined by the O'Brien-Fleming boundary with overall 2.5% 1-sided significance level will be used.

Note: Two years after the last patient accrual, on 19 May 2017, the final OS analysis was done based on a total of 195 death events (i.e., 76.5% of the 255 randomized patients): 123 events in Arm A (plitidepsin plus dexamethasone) and 72 events in Arm B (dexamethasone). Then, the duration of this study is prolonged for six additional months, until 19 November 2017, in order to continue follow-up in the alive patients, and then to be able to reach the pre-specified total of 80% of death events (approximately 204 death events) or even more. If the required death

events are not achieved on 19 November 2017, the study might be further extended by three to six months.

It is anticipated that an indeterminate number of patients in the control arm will switch treatment after progression to plitidepsin plus dexamethasone. This could cause the size of the effect on OS to be difficult to interpret. Consequently, if the OS results show to be substantially influenced by crossover, the Sponsor will study the estimated effect of crossover by means of rank preserving structural failure time models for correcting for treatment changes (68).

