6.2.3 Secondary analyses

Overall survival:

Although the study is powered for the evaluation of the main endpoint PFS, two analyses of OS will be performed to ascertain if a trend in OS is observed in favor of the experimental arm. A first analysis of OS will be performed concomitantly with the final PFS analysis. In addition, a second analysis of OS will be performed when 80% death events (approximately 200 death events) have occurred or 24 months after the inclusion of the last patient, whichever occurs first. At the interim OS analysis the significance level determined by the O'Brien-Fleming boundary with overall 2.5% 1-sided significance level will be used.

OS analyses will be performed according to the Kaplan-Meier method and the unstratified and stratified log rank tests will be used in order to ascertain if clinically significant OS effect in favor of the experimental arm is observed.

It is anticipated that an indeterminate number of patients in the control arm will switch treatment after progression to plitidepsin plus dexamethasone. This could cause the size of the effect on OS to be difficult to interpret. Consequently, if the OS results show to be substantially influenced by crossover, the Sponsor will study the estimated effect of crossover in a first sensitivity analysis excluding the patients who crossed over and a second analysis censoring survival at the time of crossover. Estimates of the unbiased effect in survival will be studied by means of, rank preserving structural failure time (RPSFT)

models for correcting for treatment changes (2), by the inverse probability of censoring weighting (IPCW) method (6) and by means of the two-stage method proposed by Latimer *et al.* (7) in order to try to control any bias caused by treatment crossover.

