
15 Revision History

From Statistical Analysis Plan v5.0 to v6.0:

This amendment of the Statistical Analysis Plan (SAP) is intended to incorporate an additional overall survival sensitivity analysis in order to better characterize the impact of crossover in arm B. The addition of this new analysis was consulted and agreed with the EMA Product Team Members in a clarification meeting that took place on 12th of June of 2017.

The nature of these analyses is supportive for the secondary analyses of overall survival already described in previous versions of the SAP.

Rational of changes:

In order to improve the characterisation of the actual impact of crossover in those patients who switched from DXM (Arm B) to plitidepsin plus DXM (Arm A), an analysis based on the two-stage method proposed by Latimer *et al.* (7) is performed.

Briefly, the two-stage estimation is a method that provides a good fit to the treatment change mechanics often observed in oncology. Usually, switching is only permitted after disease progression, but this is likely to occur shortly afterwards. In that case, disease progression can be used as a secondary baseline for patients in the control group. Fitting a Weibull model would be expected to produce a reasonable estimate of the effect resulting from switching to the experimental treatment, provided that 1) the model fits the data, 2) “no unmeasured confounders” are present at the secondary baseline, and 3) switching occurs soon after the secondary baseline. The resulting acceleration factor associated with treatment change could then be used to “shrink” survival times in switching patients to derive a counterfactual survival dataset upon which standard survival analysis could be undertaken.

CHANGES:

Included changes are highlighted in *Italic Bold*.

PAGE 16-17: Section 6.2.3 Secondary analyses – Overall survival

Original text:

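### Crossover adjustment of OS hangs on the OS results without a criterion, has no stated lead among five methods, and includes an exclusion analysis biased towards Arm A

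*Protocol*

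**What the plan says.** Protocol 10.2.3.4 expects an unknown number of Arm B patients to switch to plitidepsin plus dexamethasone after progression, and then sets the condition: "if the OS results show to be substantially influenced by crossover, the Sponsor will study the estimated effect of crossover". The only method it names is RPSFT. It does not define a substantial influence, sets no threshold, and names no decision-maker other than the Sponsor.

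SAP 6.2.3 keeps the condition but widens the methods. The effect is to be studied "in a first sensitivity analysis excluding the patients who crossed over and a second analysis censoring survival at the time of crossover". It then names RPSFT, inverse probability of censoring weighting (IPCW) and a two-stage method as ways to estimate an unbiased effect. None of the five is ranked.

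On timing, the note in Protocol 10.2.3.4 reads: "Two years after the last patient accrual, on 19 May 2017, the final OS analysis was done". It reports 195 deaths among 255 randomized patients. SAP section 15 (v5.0 to v6.0) says that the two-stage analysis was agreed with EMA team members "in a clarification meeting that took place on 12th of June of 2017", and calls it supportive. It does not mention the analysis of 19 May 2017.

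Other parts of the SAP bear on this:
- Section 4.2 assigns all OS analyses to All Randomized Patients.
- Section 6.2.3 puts the log-rank comparison before any adjustment.
- Section 8.7 makes no multiplicity adjustment for secondary analyses beyond the sequential OS looks.
- Section 11.3.4.1 gives each method its own table, with log-rank and hazard-ratio p-values, and adds forest plots of the hazard ratios.

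**The concern.** The condition is close to circular. OS results do not by themselves show how far crossover moved them; that needs the adjustment whose use is being decided. The decision is also taken with the unadjusted result in view. Since switching was expected from the start, nothing required the choice to wait for results.

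The methods rest on different assumptions, and the SAP does not say which one the reader should rely on if they disagree. Excluding switchers is the weakest of them. Only Arm B patients can be excluded, and they must have survived to progression and to at least eight weeks from randomization before they can switch. Removing them leaves Arm B with too many early deaths. The SAP is alert to prognostic differences: section 6.2.3 plans a baseline comparison of switchers and non-switchers to rule out a better prognosis in switchers. Yet the exclusion analysis carries no caveat.

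At stake is how survival is interpreted. Control patients may receive plitidepsin, so discussion of any survival benefit will lean on an adjusted hazard ratio.

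**Working it through.** **1. The plan's own OS figures.** 195/255 = 76.5%; 0.80 × 255 = 204; 0.80 × 250 = 200. All agree with the text. The documents give no sizing for OS and no expected crossover rate, so any statement of size needs assumed inputs.

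**2. The two documents side by side.**

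| Item | Protocol 10.2.3.4 | SAP 6.2.3 |
|---|---|---|
| Trigger | OS results show influence | Same |
| Criterion | None | None |
| Methods | RPSFT | Exclusion, censoring at crossover, RPSFT, IPCW, two-stage |
| Stated lead | RPSFT, as the only one | None |
| Rule if results conflict | Not needed | None |

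**3. Timing.** From 19 May to 12 June 2017 is 12 + 12 = 24 days. SAP v6.0 is undated in the supplied text, so the order rests on the meeting date.

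**4. What selection alone could do.** If five valid one-sided 2.5% tests were available and the best were taken, the error would be at most 5 × 2.5% = 12.5%, or 1 − 0.975⁵ = 11.9% if they were independent. These methods are correlated, and the RPSFT test of no effect normally keeps the ITT p-value, so the true figure for valid methods would be lower. A biased method can exceed the bound by itself.

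**5. Null simulation, method by method.** Assumed inputs: 170 vs 85 patients; median OS 11 months; median PFS 2 months; censoring uniform over 24–60 months; no treatment effect in either arm. An Arm B patient still under observation at the later of progression and 8 weeks switches with probability 0.3, 0.5 or 0.7. A shared multiplier on both times has log SD 0 or 0.5. The test is Z = (O − E)/√V, rejecting in favour of Arm A if Z < −1.96; 4,000 trials per row.

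| Arm B switching | Log SD | ITT | Exclude switchers | Censor at crossover |
|---|---|---|---|---|
| 24.6% | 0 | 2.6% | 8.3% | 3.1% |
| 24.1% | 0.5 | 2.9% | 8.4% | 2.6% |
| 40.9% | 0 | 3.0% | 16.9% | 2.9% |
| 40.3% | 0.5 | 2.8% | 18.3% | 2.3% |
| 57.2% | 0 | 2.6% | 41.3% | 2.7% |
| 56.5% | 0.5 | 2.6% | 41.8% | 1.8% |

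The simulation standard error near 2.5% is √(0.025 × 0.975/4000) = 0.25 points.

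**6. Does choosing among methods add to this?** A second null set-up used 167 vs 83 patients, median PFS 12 weeks, median post-progression survival 40 weeks, crossover after week 8, 30–32 switchers and 222–237 deaths per trial, with 600 trials per row.

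| Prognostic heterogeneity (log-hazard SD) | Exclusion alone | Any of exclusion, censoring, two-stage |
|---|---|---|
| None | 10.5% | 10.7% |
| 0.5 | 14.3% | 14.3% |
| 0.5, fitter patients switch | 21.5% | 21.5% |
| 0.7, fitter patients switch | 40.2% | 40.5% |

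Choosing among the three adds at most 40.5 − 40.2 = 0.3 points.

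**7. Dependence on inputs.** A further run with the same medians (3,000 trials per scenario; exclusion and censoring only) put the chance that at least one was significant at 5% for 40% uptake without heterogeneity. At 60% uptake it was 8% without heterogeneity, 15–35% with SD 0.5, and 54% with SD 0.7 and fitter patients switching. Censoring stayed at 1–4% and ITT, at 60% uptake, at 2.8–2.9%. RPSFT and IPCW were not simulated.

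**The case against.** The strongest reply is that little here can be hidden and no formal claim depends on it. OS is secondary and unpowered, examined for a trend. The ITT log-rank comparison comes first. Every adjusted method has its own table and Kaplan-Meier plot, forest plots set the hazard ratios together, and SAP Appendix I has all tables created at each planned analysis where applicable. IPCW covariates are listed in advance. The two-stage addition is documented, agreed with the EMA and called supportive; the v6.0 rationale describes it as performed, without repeating the condition. RPSFT is the Protocol's only method and stands first among the SAP's three estimates of an unbiased effect.

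Most of this stands, and it rules out three stronger readings.
- A reader might infer that the Sponsor could show the best of five hazard ratios and withhold the rest. The reporting plan does not support that; what remains open is which result the conclusions stress.
- A reader might infer that the late two-stage addition was a quiet choice made to suit the result. The documented EMA agreement does not support that.
- A reader might take the large false-positive rates as the cost of choosing among methods. They are almost wholly the bias of the exclusion analysis.

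The reply does not supply a criterion for the trigger or a rule for conflicting results. Being listed first does not make RPSFT the stated lead. EMA agreement does not make an analysis prespecified for data already analysed.

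**Conclusion.** The point holds, as one about a results-dependent trigger, an unstated lead method and an unlabelled late addition. That the Sponsor judges the trigger is an inference: the text says the results will show influence, and names nobody else to decide.

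The measurable hazard is the exclusion analysis. With no OS effect it alone falsely favours Arm A in about 8% of trials when roughly a quarter of Arm B switches, 17–18% at about 40%, and 41–42% at 56–57%. The corresponding figures are about 3% for ITT and 1–4% for censoring at crossover. Other assumptions about uptake and prognostic selection move the rate below or above that range. All inputs are assumptions, not trial data, and the second set-up produces more deaths (222–237) than the 195 observed. No claim is made about the error rates of RPSFT or IPCW.

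This should be corrected, but because OS is secondary and ITT comes first, it does not undermine the trial's primary conclusion.

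**What to change.** In Protocol 10.2.3.4 and SAP 6.2.3:

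1. Delete the condition on the OS results.
2. Name RPSFT, the Protocol's method, as the lead crossover-adjusted OS analysis. Run it whatever the unadjusted result and report it with the ITT log-rank p-value, for the 19 May 2017 data and for any OS update from the follow-up extended to 19 November 2017 or later.
3. Report exclusion, censoring at crossover, IPCW and two-stage together as supportive estimates without significance claims, noting beside the exclusion analysis that it is biased towards Arm A.
4. In SAP sections 6.2.3 and 15, state that the two-stage method was added after the 19 May 2017 analysis with EMA agreement. It is post hoc for that analysis, though it may pre-date a later OS update.

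The cost is wording only, since the table shells exist. New wording cannot restore prespecification for the May 2017 data, but it fixes how those results are re-reported and how later data are handled. The Sponsor gives up discretion over when to run the adjustment and which result to emphasise.

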10.2.3.5 Other Analyses of Efficacy

Efficacy parameters versus baseline covariates will be analyzed and appropriate tests will be used (i.e., the Fisher exact test and logistic regression for categorical variables, the log-rank test or Cox regression for time-to-event variables, etc.).

Exploratory intrapatient comparison of response and PFS (before and after crossover) will be performed for patients who switch from Arm B to Arm A after disease progression.

10.2.4 Pharmacokinetics

Pharmacokinetic parameters will be calculated using population methods, after pooling data from this study with data obtained in other plitidepsin single-agent studies. The effect of dexamethasone on the plitidepsin pharmacokinetics will be evaluated by testing the improvement in the "Objective Function" of the population model after the inclusion of a shift variable on every relevant PK parameter. Bayesian estimation of the individual PK parameters will be correlated with toxicity and response outcomes. Logistic regression will be used for dichotomic or categorical outcomes, such as response/no response or toxicity grade. For continuous outcomes, such as transaminase values, linear regression will be applied. The influence of the plitidepsin PK on time to event variables, such as PFS, will be evaluated using Cox regression.

10.3 INTERIM ANALYSIS

Protocol-specified analyses are foreseen at the time of the futility evaluation (approximately 40 evaluable patients for response in Arm A), final PFS analysis (main endpoint, approximately 210 progression or death events) and follow-up evaluation of OS when 80% of death events (approximately 200 death events) have occurred or 24 months after the inclusion of the last patient, whichever occurs first. Accrual will be onhold while data for the futility analysis is being assessed.

Note: Two years after the last patient accrual, on 19 May 2017, the final OS analysis was done based on a total of 195 death events (i.e., 76.5% of the 255 randomized patients): 123 events in Arm A (plitidepsin plus dexamethasone) and 72 events in Arm B (dexamethasone). Then, the duration of this study is prolonged for six additional months, until 19 November 2017, in order to continue follow-up in the alive patients, and then to be able to reach the pre-specified total of 80% of death events (approximately 204 death events) or even more. If the required death events are not achieved on 19 November 2017, the study might be further extended by three to six months.

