	Approximately 210 progression or death events would be needed in this trial to detect a HR of 0.625 in favor of the combination arm (equivalent to an increase of 60% in PFS, i.e., from 10 to 16 weeks, from 12 to 19.2 weeks, from 16 to 25.6 weeks, etc.) with 90% power and 1-sided 2.5% significance level. As a preliminary hypothesis, it is estimated that up to 250 randomized patients will be needed to achieve the 210 events in 24-30 months.						
	Statistical Analyses						
	All randomized patients during the trial will be included in the final efficacy analyses, while the first 40 patients evaluable for response in Arm A will be included in an early futility analysis. A response rate (IMWG criteria) of at least 30% (twelve or more responses by IRC review) will be taken as threshold for continuation of the study. A minimum response rate of 30% has been considered as clinically significant in this setting. This result will ensure that the lower limit of the exact binomial 95% Confidence Interval for the response rate will be greater than 15% (95% CI in case of 12 responses would be 16.6% - 46.5%).						
	No claim for superiority in efficacy will be formulated in this interim analysis and no alpha-spending for the analysis of PFS is foreseen.						

	The main analysis will be conducted after 210 progression and/or death events are observed. The PFS assessed by the IRC will be used for the primary analysis, while the Investigator assessment will be used for the secondary analysis of PFS.
	An interim analysis of OS will be performed concomitantly with the final PFS analysis. A final analysis of OS will be performed when 80% of death events (approximately 200 death events) have occurred, or 24 months after the inclusion of the last patient, whichever occurs first.
	Note: Two years after the last patient accrual, on 19 May 2017, the final OS analysis was done based on a total of 195 death events (i.e., 76.5% of the 255 randomized patients): 123 events in Arm A (plitidepsin plus dexamethasone) and 72 events in Arm B (dexamethasone). Then, the duration of this study is prolonged for six additional months, until 19 November 2017, in order to continue follow-up in the alive patients, and then to be able to reach the prespecified total of 80% of death events (approximately 204 death events) or even more. If the required death events are not achieved on 19 November 2017, the study might be further extended by three to six months.

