	The unstratified log-rank test will be used to compare the PFS of Arm A and B. A stratified log-rank test for the main endpoint (PFS) will be performed as supportive analysis.
	Secondary time-to-event endpoints (DR, OS) will be analyzed according to the Kaplan-Meier method and compared between treatment groups using the log-rank test.
	Counts and percentages, with their corresponding exact 95% confidence intervals, will be calculated for the response rate (IMWG criteria and, separately, minor response). The Fisher's exact test will be used to compare the RRs of Arm A and B.
	Both the IRC and Investigator's assessments will be used for RR, PFS and DR.
	Efficacy parameters vs. baseline covariates will be analyzed and appropriate tests will be used (i.e., Fisher's exact test and logistic regression for categorical variables; the log-rank test or Cox regression for time-to-event variables, etc.).
	Exploratory intrapatient comparison of response and PFS (before and after crossover) will be performed for patients who switch from Arm B to Arm A after disease progression.
ANTICIPATED	 Protocol submission: 1Q2010.
STUDY DATES	 Planned start date (first patient on study): 2Q2010.
	• Complete enrollment: 60 months (2Q2010-2Q2015).
	 Planned study termination date: it will be set after the occurrence of 80% of death events, 24 months after the accrual of the last randomized patient, or IDMC recommendation (whichever occurs first).
	Note: Two years after the last patient accrual, on 19 May 2017, the final OS analysis was done based on a total of 195 death events (i.e., 76.5% of the 255 randomized patients): 123 events in Arm A (plitidepsin plus dexamethasone) and 72 events in Arm B (dexamethasone). Then, the

duration of this study is prolonged for six additional months, until 19 November 2017 , in order to continue follow-up in the alive patients, and then to be able to reach the pre-specified total of 80% of death events (approximately 204 death events) or even more. If the required death events are not achieved on 19 November 2017, the study might be further extended by three to six months.
The futility analysis is foreseen after 40 patients evaluable for response are recruited in Arm A, approximately 12 months after the recruitment start.
All patients on active treatment at the date of study termination will be offered to continue to receive plitidepsin-based treatment off-study according to the Investigator's criteria and upon Sponsor agreement.

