- 16. Bone marrow evaluation, radiological tumor assessment and skeletal evaluation will be performed only on pre-treatment and treatment evaluations. These evaluations will not be performed after the end of treatment. After the end of treatment, all patients will be followed every three months for survival until death, or until the date of study termination. The follow-up visits will be performed by phone only if the patient is unable to go to the study center owing to the seriousness of his/her disease. This will only apply to patients who are followed up after discontinuing treatment due to disease progression.
- 17. May be evaluated using CT-scan or X-ray, provided the same procedure is used throughout the study.
- 18. Optional substudy (a separate ICF needs to be signed).

Note: One patient was still undergoing treatment on 19 May 2017. However, as the primary endpoint of the study (progression-free survival) was fulfilled, and this extended follow-up is focused only on survival, no information such as central laboratory data or images will be sent for independent review. Nevertheless, laboratory determinations or images will be done locally, if clinically indicated, in order to perform tumor assessment.

Hematology: Differential white blood cells (WBC), hemoglobin, hematocrit and platelets.

Biochemistry A: AST, ALT, total bilirubin, direct bilirubin in case total bilirubin is above ULN, alkaline phosphatase (AP), creatinine, calculated creatinine clearance (Cockcroft and Gault's formula; see Appendix 3), glucose, serum electrolytes (Na⁺, K⁺, Mg⁺⁺, Ca⁺⁺), creatine phosphokinase (CPK), CPK-MB fraction (should be measured only if CPK is abnormally high) and troponin I.

Biochemistry B: Uric acid, lactate dehydrogenase (LDH), total proteins and albumin.

Coagulation tests: PT, PTT and INR.

e Events

LIST OF ABBREVIATIONS AND DEFINITION OF TERMS

БСНО	Tak seendia seen
ECHO	Echocardiogram
ECOG	Eastern Cooperative Oncology Group
EOI	End of Infusion
EPO	Erythropoietin
ER	Endoplasmic Reticulum
EU	European Union
GC	Glucocorticoids
GCP	Good Clinical Practice
G-CSF	Granulocyte Colony Stimulating Factor
GGT	γ-Glutamyltranspeptidase
GI	Gastrointestinal
GM-CSF	Granulocyte/Macrophage Colony Stimulating Factor
GMT	Greenwich Mean Time
GR	GC Receptor
GSH	Gluthatione Reduced
h	Hour(s)
НАТ	Histone Acetyltransferase
Hb	Hemoglobin
HBV	Hepatitis B Virus
HCG	Human Chorionic Gonadotropin
HCV	Hepatitis C Virus
HDAC	Histone Deacetylase
HIV	Human Immunodeficiency Virus

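### Does extending follow-up after the final overall-survival analysis leave room for an unplanned third test?

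*Protocol*

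**What the plan says.** Protocol section 10.2.3.4 plans two OS analyses to look for a trend in favour of the combination. The interim accompanies the final PFS analysis. The final comes at 80% of deaths (about 200) "or 24 months after the inclusion of the last patient, whichever occurs first". For the interim, "the significance level determined by the O'Brien-Fleming boundary with overall 2.5% 1-sided significance level will be used". SAP sections 5.2 and 6.2.3 say the same. The study termination date follows a similar first-to-occur rule, with an IDMC recommendation as a third trigger (protocol Synopsis, 5.1, 5.5 and 5.13; SAP 6.1.2).

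A Note, repeated in the Synopsis and in sections 5.1, 5.5, 5.13, 10.2.3.4 and 10.3, reports that on 19 May 2017, two years after the last accrual, "the final OS analysis was done based on a total of 195 death events". It continues that "the duration of this study is prolonged for six additional months", with 19 November 2017 as the new date. The stated purpose is "in order to continue follow-up in the alive patients, and then to be able to reach the pre-specified total of 80% of death events" (about 204, or more). It closes: "If the required death events are not achieved on 19 November 2017, the study might be further extended by three to six months". The notes to the schedule of assessments and to Table 4 (section 5.11) add that "this extended follow-up is focused only on survival".

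SAP Appendix I says that its tables are produced at each planned analysis, where applicable, and again at the end of the study. The main OS table (11.3.4.1.1) has a log-rank p-value column.

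**The concern.** Three features together look like a problem.

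- **The trigger had already been used.** The 24-month limb came first, the final OS analysis followed, and the two-look O'Brien-Fleming plan was complete. After that no rule demanded 80% of deaths, yet the Note calls that count pre-specified and required.
- **The status of later OS output is not written down.** No sentence says that OS results from the extension are descriptive. If the end of the study means the extended date, Appendix I would print a fresh log-rank p-value with no alpha behind it.
- **The extension follows the final analysis.** The new horizon appears in the same Note that reports the 195 deaths by arm.

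At stake is the OS type I error. A reader might take a p-value at about 204 deaths for the planned 80% analysis and judge it against a boundary already spent at 195.

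**Working it through.** **The plan's own counts.** From the Note: 123 + 72 = 195 deaths; 195/255 = 76.5%; 0.80 × 255 = 204. The figure of about 200 in the rule is 0.80 × 250, the planned sample size. Since 195 is below both 200 and 204, the 24-month limb was the one met. Reaching 204 needs 204 − 195 = 9 more deaths among the 255 − 195 = 60 patients not counted as dead.

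**Is a third test planned?** Setting the texts side by side:

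| Place | What it implies |
|---|---|
| Protocol 10.2.3.4, SAP 6.2.3 | Two OS analyses, no more |
| The Note | The second, final one is complete |
| Notes to the schedule of assessments and Table 4 | The extension collects survival |
| SAP 6.2.3, current text (version 6.0 cites a meeting of 12 June 2017, after the final OS analysis) | Adds a supportive crossover method; no further look and no further boundary |
| SAP Appendix I | A general instruction covering every table |
| SAP 6.1.2 | Study termination is first-to-occur, so within the SAP the study's end coincides with the 24-month limb |

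Nothing here schedules a test at 204 deaths. Appendix I reaches the extended date only if the end of the study is read against the SAP's own definition.

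**How long is the extension?** The Note gives 19 November 2017 and then at most six more months, so the latest stated end is about 19 May 2018. The calendar limit is stated; only the death count is left open.

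**Size if someone tested anyway.** Successive log-rank statistics are treated as multivariate normal with correlation √(dᵢ/dⱼ). The number of deaths at the interim, d₁, is not in the documents, so 80 to 175 is assumed. The boundaries are c·√(195/d₁) at the interim and c at 195 deaths, with c solved so that P(Z₁ > c·√(195/d₁) or Z₂ > c) = 0.025. One more reading is then added at 204 deaths against the same c; its correlation with the 195-death statistic is √(195/204) = 0.978.

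| d₁ (assumed) | c at 195 | Nominal one-sided level at 195 | Error with a reading at 204 | Excess over 2.5% (points) |
|---|---|---|---|---|
| 80 | 1.968 | 2.46% | 2.979% | 0.479 |
| 100 | 1.979 | 2.39% | 2.963% | 0.463 |
| 120 | 1.995 | 2.30% | 2.939% | 0.439 |
| 140 | 2.011 | 2.22% | 2.912% | 0.412 |
| 160 | 2.023 | 2.15% | 2.884% | 0.384 |
| 175 | 2.026 | 2.14% | 2.867% | 0.367 |

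With the plan followed as written, the last two columns do not arise and the OS error stays at 2.5%.

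**The case for a change.** The best case for a change is that the inconsistency is in current protocol text and exists whether or not anyone retests. A count that was one of two alternatives is called required after the other alternative has been met, and the SAP's termination definition carries no mention of the extension. A p-value at the extended date can be printed under Appendix I, SAP 8.7 makes no adjustment beyond the sequential OS looks, and the Note's wording makes it easy to mistake that p-value for the planned 80% analysis. One sentence calling later output descriptive would be cheap.

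The factual part stands: the word is loose, and SAP 6.1.2 was not aligned with the Note. The consequence does not follow. Eighty percent was indeed specified in advance, as one limb, and required can be read as the deaths needed to reach it. Within the protocol the Note sits beside the termination rule wherever that rule is stated, so the extension is in plain view. A refreshed p-value on a table shell is not a significance claim. The SAP already prints p-values on many supportive OS tables (crossover patients excluded, crossover patients censored, IPCW, RPSFT, two-stage), and no one would read those as confirmatory. Looking for a trend does not by itself settle the status of later output, because it sits beside a formal 2.5% boundary. The completed final analysis and the fixed number of looks do settle it.

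**Conclusion.** No change follows. The Note has a clerical slip in describing 80% of deaths as required, and the status of later OS output is a gap that an analyst fills sensibly: inference rests on the 195-death analysis, and anything from the extension is an update with longer follow-up. As written, the plan has two OS looks and a one-sided error of 2.5%.

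The excess of 0.37 to 0.48 percentage points depends on a third reading at exactly 204 deaths that no section proposes, on reuse of a final boundary that the documents do not state, and on an assumed interim of 80 to 175 deaths. OS is a secondary endpoint for which the study was not powered, and the primary PFS test is unaffected. Extra survival follow-up in up to 60 patients is useful in itself. Rewording would tidy the text without altering any analysis or result.
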